## 1 Background

Lung cancer is currently one of the most common malignant tumors in the world, and Non-small Cell Lung Cancers (NSCLC) accounts for 80%-85% of all lung cancer patients, among them about 75% of them are in the middle and advanced stage when they are discovered, and the 5-year survival rate is very low. At present, the treatment of lung cancer patients is based on chemotherapy combined with targeted drug therapy in clinical. The effective rate of first-line chemotherapy is only about 30%, and it has high toxicity and adverse reactions, so its application is limited.

Targeted drug therapy-related genes are key genes in the process of lung cancer cell differentiation, proliferation, apoptosis, migration, etc. These gene mutations will continue to activate related signaling pathways, leading to the occurrence and development of tumors, mutations in these genes can be detected in tumor cells of almost all histological types of lung cancer patients. Targeted therapy can provide a basis for the diagnosis and postoperative drug adjuvant treatment of NSCLC patients, and the formulation of drug selection and treatment plans for advanced patients based on the genetic mutations of NSCLC patients.

Wherein, in the treatment of non-small cell lung cancer, the main molecular targeted therapy is epidermal growth factor receptor (EGFR). The efficacy of molecularly targeted drugs is significantly different between different lung cancer patients of the same tissue type and different lung cancer pathological tissue types. The EGFR mutation rate in Asian patients with advanced lung adenocarcinoma is as high as 50%, and there are many EGFR tyrosine kinase inhibitor (TKI) is listed in China and used for clinical treatment. In addition to EGFR, anaplastic lymphoma kinase (ALK) fusion gene and ROS1 fusion gene are also divided into subgroups of NSCLC molecules with specific clinical and pathological characteristics, thereby providing new molecular targets for the treatment of lung cancer. In addition, biomarkers related to lung cancer include HER2, KRAS, BRAF V600E gene mutations, and MET exon 14 skipping mutations. At present, the molecular classification of lung cancer plays an important role in guiding clinical treatment plans, drug selection, and establishing an individualized treatment model for molecular classification. Patients with specific genotypes can only benefit from the corresponding targeted drugs. Therefore, effective and accurate detection of tumor gene status and accurate molecular

subtype differentiation of NSCLC patient populations have become an important basis for patient treatment, prognosis evaluation, and efficacy monitoring.

At present, the routine detection methods for clinical gene detection are fluorescent quantitative PCR, nucleic acid sequence determination, FISH and so on. However, to carry out the above-mentioned gene detection at the same time requires the combination of multiple technology platforms and multiple methods. The large sample size requirements, the complex operation process, and the long detection cycle pose very high challenges to personnel, technology, equipment, etc., which is a serious departure from the clinical goal of quickly and accurately obtaining patient clinical medication information.

The Genetron Lung Cancer Panel is developed by Genetron Health (Beijing) Co., Ltd.. It is used to detect EGFR, KRAS, BRAF, HER2, PIK3CA, ALK, ROS1, MET gene mutations or fusions in non-small cell lung cancer patients. The Genetron Lung Cancer Panel is prepared in a clean production workshop that meets the requirements of the "In Vitro Diagnostic Reagent Production Implementation Rules", and has passed the self-test.

## 2 Research Purpose

The main purpose of this study is: by evaluating the Genetron Lung Cancer Panel to compare the results of simultaneous detection with similar products on the market and the Sanger sequencing method, and to calculate the coincidence rate and consistency of the assessment reagents and the comparison method. The safety and effectiveness of the product are confirmed and evaluated. Meanwhile, the accuracy of the Genetron Lung Cancer Panel for the following drug companion diagnostic tests: EGFR gene 19 exon deletion and L858R point mutation in gefitinib tablets, erlotinib hydrochloride and icotinib hydrochloride tablets, T790M point mutation in methanesulfonate acid osimertinib tablets, ALK gene fusion and ROS1 gene fusion in crizotinib capsules.

## 3 Trial Design

#### 3.1 Overall Design of the Trial

This trial follows the principle of synchronous blinding. The enrolled cases are coded, and the enrolled samples are detected with the Genetron Lung Cancer Panel and comparison methods. The

detection results are compared, and the samples that are inconsistent with the detection results of similar products on the market are reviewed by the Sanger sequencing method, when the site detection results compared with Sanger sequencing method are inconsistent, Sanger's detection results are recognized. The results were determined independently according to the cutoff values or interpretation requirements provided by each method, and relevant statistics were used to evaluate clinical application performance of

Genetron Lung Cancer Panel.

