### 4 Statistical Analysis

#### 4.1 The coincidence rate of the panel and the comparison method

For each gene locus, a four-grid table was used to calculate the positive coincidence rate, negative coincidence rate, positive predictive value, negative predictive value, total coincidence rate and 95% confidence interval of the assessment reagent and the comparison method. Using statistical software, Kappa test is used to determine whether the two detection methods are statistically significant.

Table 2. Results statistics

Genetron Lung Cancer	Comparison method		Total
Panel	Positive	Negative	
Positive	A	В	A+B
Negative	C	D	C+D
Total	A+C	B+D	A+B+C+D

A sample with a mutation genotype is judged as positive, and a sample with no mutation genotype is judged as negative

The calculation formula is:

Positive coincidence rate=A/(A+C)×100%

Negative coincidence rate =  $D/(B+D) \times 100\%$ 

Positive predictive value (PPV)=A/(A+B)×100%

Negative predictive value (NPV)=D/(C+D)×100%

Total coincidence rate=(A+D)/(A+B+C+D)×100%

95% confidence interval calculation formula:  $p\pm1.96\times[p(1-p)/n]^{1/2}$  (where p is the positive coincidence rate, negative coincidence rate, positive predictive value, negative predictive value, total coincidence rate, n is the sample size, if p>0.9, use Wilson score method for correction).

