#### 4.2 Kappa test

The Kappa test method was used to analyze the equivalence of clinical research reagents and comparison methods. Using statistical software, Kappa test was performed on the detection results of clinical research reagents and gold standard, and the k value was calculated. When k>0.75, clinical research reagents and comparison methods have good consistency.

$$Kappa = \frac{P_a - P_c}{1 - P_c}$$
, Where  $P_{a=} = \frac{A + D}{N}$ ,  $P_C = \frac{(A + B)(A + C)}{N} + \frac{(B + D)(C + D)}{N}$ 

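### The plan does not say whether a Sanger review result may replace the comparator's on discordant samples in Table 2 and kappa; if it does so at the discordant site only, every agreement point estimate rises or stays equal

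*Combined protocol and SAP*

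**What the plan says.** Section 2 gives the aim as "to calculate the coincidence rate and consistency of the assessment reagents and the comparison method". It names both similar marketed products and Sanger as the methods to compare with.

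Section 3.1 says that "samples that are inconsistent with the detection results of similar products on the market are reviewed by the Sanger sequencing method", then that "when the site detection results compared with Sanger sequencing method are inconsistent, Sanger's detection results are recognized". The next sentence turns to the evaluation: "The results were determined independently according to the cutoff values or interpretation requirements provided by each method".

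Section 3.3.2 (Table 1) lists a marketed kit for EGFR, ALK, ROS1, KRAS, PIK3CA and BRAF. ROS1 has a FISH probe and, on at least 200 samples, a PCR kit as well. MET and HER2 have no kit; the instrument list under 3.3.2 assigns them Sanger. Section 3.3.3 makes Sanger the review method and allows further verification methods to be added.

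Section 4.1 begins "For each gene locus, a four-grid table was used" and asks for the "total coincidence rate and 95% confidence interval of the assessment reagent and the comparison method". Section 4.2 says "Kappa test was performed on the detection results of clinical research reagents and gold standard", but words its criterion of k above 0.75 as showing that "clinical research reagents and comparison methods have good consistency".

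**The concern.** No sentence says which result fills cells A to D once a discordant sample has been reviewed. Recognizing the Sanger result may mean overwriting the comparator's call, or only recording which method Sanger supported. The undefined gold standard in 4.2 could be either. Two analysts following the text could report different coincidence rates and kappa from the same data, including for EGFR, ALK and ROS1, the companion-diagnostic genes named in section 2.

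The two choices are not symmetric. Review is triggered only by disagreement, so shared errors of panel and comparator are never re-examined and nothing offsets the gain from re-examining the rest. Figures built this way would mix comparator and selectively applied Sanger results while being labelled as agreement with the comparison method.

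**Working it through.** **Which reference do the passages support?**

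- For the original comparator: the aim in section 2, the 4.1 heading and opening sentence, the Table 2 column header, two mentions of comparison methods in 4.2, and the separate label of review method for Sanger in 3.3.3.
- For the Sanger-resolved result: the recognition clause in 3.1, placed just before the statistics, and the gold standard in 4.2.
- Neither reading is stated as a rule, and no section asks for tables both before and after review.

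**Direction.** Suppose Sanger replaces the comparator at the discordant site only. Rows are the panel's call and columns the reference, so a result in B (panel positive, reference negative) moves to A if Sanger is positive and otherwise stays. A result in C moves to D if Sanger is negative and otherwise stays.

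| Measure | B to A | C to D |
|---|---|---|
| A/(A+C) | rises or equal | rises or equal |
| D/(B+D) | rises or equal | rises or equal |
| A/(A+B) | rises | unchanged |
| D/(C+D) | unchanged | rises |
| (A+D)/N | rises | rises |

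Kappa was checked as (Pa − Pc)/(1 − Pc), with Pa = (A+D)/N and Pc = [(A+B)(A+C) + (B+D)(C+D)]/N². The text of 4.2 as extracted shows N where the standard form has N²; the exponent may have been lost, and N² is used here. In exact enumeration of all tables with N from 2 to 20 and every possible replacement (219,602 cases), none of the six measures ever fell.

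**Size.** N = 1052 is from section 3.2.1. Its minimum of 30% positive samples is borrowed as one locus's positive rate: 0.30 × 1052 ≈ 316. All cell counts and siding rates below are assumed.

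*Main illustration, A/B/C/D = 284/22/32/714.*
- Positive coincidence: 284/316 = 89.9%.
- Pa = 998/1052 = 0.9487; Pc = (306×316 + 736×746)/1052² = 645,752/1,106,704 = 0.5835.
- Kappa = (0.9487 − 0.5835)/(1 − 0.5835) = 0.877.

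If Sanger sides with the panel in half of the discordants, 11 move from B to A and 16 from C to D, giving 295/11/16/730.
- Positive coincidence: 295/311 = 94.9%.
- Pa = 1025/1052 = 0.9743; Pc = (306×311 + 741×746)/1052² = 647,952/1,106,704 = 0.5855.
- Kappa = (0.9743 − 0.5855)/(1 − 0.5855) = 0.938.

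*The gain needs no information from Sanger.* From 253/54/63/682 (kappa 0.733), a Sanger read that is always negative gives 253/54/0/745 and kappa 0.869. One that is always positive gives 307/0/63/682 and kappa 0.863.

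*Crossing 0.75.* Take 20 assumed starts with 316 positives (positive coincidence 75 to 95%, negative 90 to 97%) and Sanger siding with the panel in 25% of discordants. Five cross 0.75, 14 are above it either way and one is below it either way. The five that cross have 115 to 137 discordants, that is 10.9% to 13.0% of 1052. A rare locus needs fewer: 15/6/6/1025 (21 positives) goes from 0.709 to 0.854 if half are resolved for the panel.

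**Limits of the direction result.**
- If Sanger also overrode concordant calls, agreement could fall: moving three results from A to B in the main illustration gives 281/25/32/714 and kappa 0.870, below 0.877. Review is triggered per sample, and 3.3.3 does not confine Sanger to the discordant site.
- It concerns point estimates. Section 4.1 switches from the Wald to the Wilson interval above 0.9. One B-to-A move that takes positive coincidence from 9/10 to 10/11 lowers the lower limit from 0.714 (Wald) to 0.623 (Wilson).
- MET and HER2 are unaffected, because Sanger is already their comparator.

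**The case against.** The strongest reply is that the recognition clause may not concern the marketed kits at all. Section 2 names two kinds of comparator, and 3.1 has two parallel clauses: one for disagreement with marketed products, one for disagreement with Sanger. Sites compared with Sanger could be simply MET and HER2, in which case the clause says nothing about replacing cobas, FISH or PCR results. What remains is one stray term in 4.2, between two mentions of comparison methods, and 4.1 is consistent throughout. This reading is plausible and cannot be excluded. It does not settle the matter: it leaves the gold standard undefined, and no sentence says how review results for the other six genes are reported.

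A second reply is that every magnitude is assumed, and that crossing 0.75 at a common locus takes about 11% discordance or more. That stands. So does the point that 0.75 only earns a description of good consistency, with no pass or fail rule attached.

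A reader might infer that the plan prescribes discrepant resolution, or that the reported agreement is inflated. The documents support neither: no passage orders substitution or re-tabulation, and no discordance counts are given.

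**Conclusion.** The point holds as an unresolved choice of reference with a one-directional risk, and it should be fixed. The text permits replacement of the comparator on discordant samples only but does not clearly require it; most of sections 4.1 and 4.2 favours the original comparator, and under that reading there is no effect.

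If replacement is made at the discordant site only, the six point estimates for EGFR, ALK, ROS1, KRAS, BRAF and PIK3CA cannot fall, however good or poor the Sanger read. This does not extend to every lower confidence limit, nor to replacement that also overrides concordant calls. The size cannot be derived from the documents. The main illustration gives about five percentage points of positive coincidence and 0.06 of kappa, with the consistency label unchanged. If Sanger never sides with the panel, nothing changes.

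**What to change.** - In 3.1, 4.1 and 4.2, state that the primary four-grid tables, coincidence rates, predictive values, confidence intervals and kappa use the original, unresolved result of the Table 1 comparator, with Sanger for MET and HER2.
- For ROS1, give separate tables for FISH and for the PCR kit.
- In 4.2, replace the term gold standard with comparison method.
- In 3.1, say that a recognized Sanger result does not replace the comparator's result in the primary tables.
- Report Sanger, and any verification method added under 3.3.3, on discordant samples separately by locus as a descriptive listing. Do not present it as accuracy, since concordant samples had no Sanger review.

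The cost is wording only: the same samples and the same Sanger tests serve. The downside for the sponsor is that headline agreement may be somewhat lower than under the resolved reading.

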#### 3.2.2 Inclusion Criteria, Exclusion Criteria Rejection Criteria of Study Subjects

#### 3.2.2.1 Inclusion Criteria

- (1) Clinically diagnosed as non-small cell lung cancer samples (mainly lung adenocarcinoma and some lung squamous cell carcinoma, adenosquamous carcinoma, large cell carcinoma, etc.), and a small number of other cancer types are enrolled as interference samples.
- (2) Collect some samples of relevant medical information before and after the use of targeted drugs.

  This part of the samples should have relevant previous molecular diagnosis results.

- (3) Able to provide samples in time according to the requirements of the plan: samples for DNA/RNA extraction: 10 pieces of 10 µm thickness for each sample or 10 pieces of paraffin rolls. Samples for FISH experiment: 5 slices of 3-4µm thickness.
- (4) The pathological examination conforms to the types of tissue samples listed in the above table. The HE staining results show that the tumor content is not less than 50%, and the paraffin slice damage should be avoided.
- (5) The sample should have corresponding basic clinical information, including: patient visiting number/medical record number/specimen number, age, gender, pathological diagnosis result, molecular diagnosis result (if any).

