#### Applicable instrument for comparison method

EGFR, KRAS, BRAF, ROS1 (for fluorescent PCR method): including but not limited to cobas® 4800 System, Stratagene Mx3000P, ABI7500, Bio-rad CFX96;

PIK3CA (for fluorescent PCR method): Stratagene Mx3000P

ALK, ROS1 (FISH method applicable): Break Apart FISH Probe platform;

MET, HER2 (Sanger method applicable): Life 3130/3130xl, 3730xl, 3500Dx, 3500xl Dx.

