#### 3.3.3 Review method

Sanger sequencing is used as the review method. Sequencing fragments cover the target nucleic acid segments, sites and corresponding types amplified by the assessment reagent. After the sequencing reaction is over, submit a representative sample sequencing map and result analysis data.

During the trial, different verification methods can be appropriately added according to the specific conditions.

- (1) Product name for clinical trials: Sequencing Kit (Life: BigDye Sequencing Reaction Kit)
- (2) Test equipment: Life 3130/3130xl, 3730xl, 3500Dx, 3500xl Dx

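### Section 3.1 makes Sanger final for samples where the panel and the marketed comparator disagree, whether or not Sanger could detect the mutation; if those rulings enter Table 2, the positive coincidence rate can only rise for the samples that the panel missed

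*Combined protocol and SAP*

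**What the plan says.** Section 3.1 sets the trigger for review: "the samples that are inconsistent with the detection results of similar products on the market are reviewed by the Sanger sequencing method". It then sets the decision rule: "when the site detection results compared with Sanger sequencing method are inconsistent, Sanger's detection results are recognized". Section 3.3.3 confirms the role: "Sanger sequencing is used as the review method". It requires the Sanger fragments to cover the panel's targets but sets no sensitivity requirement. It also says that "different verification methods can be appropriately added according to the specific conditions", without giving a trigger or saying that such a method would overrule Sanger.

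The only reference to thresholds is in section 3.1: "The results were determined independently according to the cutoff values or interpretation requirements provided by each method". No cutoff or detection limit is given for Sanger, the panel or any comparator. No rule covers a Sanger negative near or below its limit.

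Section 4.1 defines Table 2 and the coincidence rates against the comparison method. Section 4.2 also names a gold standard, which it does not define. Neither section says whether a Sanger ruling replaces the comparator result in the table.

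Two other places bear on the point. Section 2 lists among the companion-diagnostic claims the "T790M point mutation in methanesulfonate acid osimertinib tablets". Section 3.2.2.1 includes some samples from before and after targeted treatment.

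**The concern.** A negative result from a method that may be unable to see the mutation does not show that the comparator was wrong. Section 3.1 nevertheless lets it settle the disagreement.

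The comparator-positive, panel-negative samples (cell C) may include weak-signal ones, for example a mutation carried by only some of the tumour cells. If Sanger is less sensitive than the comparator, it may read such a sample as wild type. The panel's miss is then reclassified as a correct negative and leaves the denominator of the positive coincidence rate. For a companion-diagnostic claim such as T790M or the EGFR activating mutations, a missed mutation is the error that this rate is meant to show.

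The same weakness also works against the panel. A real weak mutation that only the panel finds, and that Sanger cannot confirm, stays in cell B and counts as a panel error.

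**Working it through.** The plan states no figure for this effect, so there is none to reproduce. The check follows what the rule does to Table 2.

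**Inputs from the document.** N = 1052 (3.2.1); positive share at least 30% (3.2.1); positive coincidence rate A/(A+C) and negative coincidence rate D/(B+D) (4.1); kappa threshold 0.75 (4.2); tumour content at least 50% (3.2.2.1).

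**Assumptions.** All 1052 samples are tested at the locus, all samples in C carry a real mutation, and Sanger's ruling replaces the comparator result. Let v be the share of C that Sanger can see. The remainder, (1 − v)C, moves from C to D, so the adjudicated rate is A/(A + vC). The counts and v are not in the documents, so a range is shown.

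**Example 1: 40 comparator positives, A = 32, C = 8, B = 0, D = 1012.** Chance agreement is taken over N². With B = 0, kappa = 2AD / [AD + (A+C)(C+D)], and C + D stays at 1020.

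| v | C left | D | Positive rate | Kappa |
|---|---|---|---|---|
| 1 | 8 | 1012 | 32/40 = 80.0% | 64768/73184 = 0.885 |
| 0.75 | 6 | 1014 | 32/38 = 84.2% | 64896/71208 = 0.911 |
| 0.5 | 4 | 1016 | 32/36 = 88.9% | 65024/69232 = 0.939 |
| 0.25 | 2 | 1018 | 32/34 = 94.1% | 65152/67256 = 0.969 |
| 0 | 0 | 1020 | 32/32 = 100% | 1.000 |

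The Wilson 95% interval is about 65% to 90% for 32/40. For 32/32 its lower bound is about 89%.

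**Example 2: 316 comparator positives (30% of 1052, rounded up), 736 negatives, B = 0.**

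| v | C = 16 at start | C = 32 at start |
|---|---|---|
| 1 | 300/316 = 94.9% | 284/316 = 89.9% |
| 0.75 | 300/312 = 96.2% | 284/308 = 92.2% |
| 0.5 | 300/308 = 97.4% | 284/300 = 94.7% |
| 0.25 | 300/304 = 98.7% | 284/292 = 97.3% |
| 0 | 100% | 100% |

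The largest rise is 5.1 points for C = 16 and 10.1 points for C = 32. Kappa starts at 0.963 and 0.925 respectively and rises to 1.000.

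**The other direction.** Put B = 16 among the 736 comparator negatives. If Sanger sees none of them, the negative coincidence rate stays at 720/736 = 97.8%. If it confirms all 16, they move to A and the rate is 720/720 = 100%. Per sample this effect is small at an uncommon locus. In example 1, one sample in B shifts negative agreement by 1/1012 = 0.1 point, while one in C shifts positive agreement by 1/40 = 2.5 points.

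**How exposed are the samples?** For a diploid heterozygous mutation, mutant fraction = tumour content × share of tumour cells carrying it / 2. At 50% content, a mutation in all tumour cells gives 0.5 × 1 / 2 = 25%; one in 40% of them gives 0.5 × 0.4 / 2 = 10%. With an assumed Sanger limit of 5%, 10%, 15%, 20% or 25%, a mutation at 50% content falls below the limit only if fewer than 20%, 40%, 60%, 80% or 100% of tumour cells carry it.

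**The case against.** A reader might infer more: that the rule is likely to erase the panel's misses at every discordant site, and always in the panel's favour. The documents do not support that reading.

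- **Likelihood.** It would require Sanger to be less sensitive than the comparator and the misses to lie at low mutant fractions. The documents give neither limits nor fractions, and do not say that T790M is subclonal in these samples. Section 3.2.2.1 also says "The HE staining results show that the tumor content is not less than 50" per cent, which makes mutations carried by all tumour cells less exposed. This objection stands, so the claim must be conditional.
- **Scope.** The instrument list under 3.3.2 has "MET, HER2 (Sanger method applicable", and Table 1 names no kit for these two genes. Sanger is their comparator, so there is nothing separate to adjudicate. ALK and ROS1 are compared with FISH, to which a mutant-fraction argument does not carry over. This also stands.
- **Direction.** Weak calls made only by the panel stay in B and lower its negative coincidence rate and positive predictive value. The effect is not one-sided.
- **Table 2.** Section 4.1 does not say that adjudicated results enter the table. If raw comparator results are used, the shift is zero. Saying that Sanger's result is recognized makes the other reading natural, but the text does not settle it.
- **Decision.** Kappa passes 0.75 before and after adjudication in every example run, and the plan sets no acceptance limit for positive coincidence. Only the reported rate moves.

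Two possible defences carry less weight. Further verification methods are permitted but not required. The sentence on each method's own cutoff governs how a result is called, not whether a negative below the limit is informative.

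**Conclusion.** The point holds in conditional form, for the mutation loci with a separate marketed comparator: EGFR, KRAS, BRAF and PIK3CA. Section 3.1 gives Sanger the last word on discordant samples without asking whether it could have seen the mutation. If its rulings enter Table 2, each comparator-positive, panel-negative sample that Sanger reads as negative moves from C to D and raises the positive coincidence rate. Where the mutation was real, that rise is a bias in the panel's favour. Where the comparator was wrong, it is a proper correction. The plan has no means of telling the two apart.

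In the assumed 40-positive example the rise is between 0 and 20 points, depending wholly on how many of the misses Sanger can see. The direction follows from the formulas in 4.1, but the size rests on assumed counts. No change in the kappa conclusion was found. This is an inexpensive improvement to how agreement is reported, not a demonstrated failure of the trial.

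**What to change.** 1. In 3.1 and 4.1, state that the primary Table 2 rates, and the kappa in 4.2, are calculated from the unadjudicated panel and comparison-method results. A Sanger-negative review then does not overturn a comparator-positive result, and the sample stays discordant.
2. Report the Sanger review as a secondary listing by direction (B and C), with Sanger-adjudicated rates as a sensitivity analysis.
3. State Sanger's detection limit in 3.3.3 where it is known.
4. Limit the rule to EGFR, KRAS, BRAF and PIK3CA. Say that it does not arise for MET and HER2, and describe the handling of FISH-compared fusions separately.

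A rule that accepts a Sanger negative only above a given mutant fraction may look more exact, but it is not workable here. A panel-negative sample has no usable fraction from the panel, and obtaining one by a quantitative method could mean extra testing.

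The cost is protocol wording, one listing and one sensitivity analysis, with no new tests. The downside is that reported agreement may be slightly lower. True comparator false positives stay counted as discordant in the primary table, as do real panel-only mutations that Sanger confirms. The sensitivity analysis shows the effect of both.
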